2.2.2. Secondary outcome

Secondary outcomes include:

- Changes in white cells blood sub-population defined by the difference between two time points: the day before adjuvant RT (day -1) to day 28 (+/- 3 days) after RT.

In particular, we will evaluate changes of:

- circulating T cells CD3+CD8+ and CD3+CD4+

- absolute lymphocyte count (ALC) and neutrophil counts (ANC) and neutrophil/lymphocyte ratio (NLR)
- Treg lymphocytes, defined as CD4+CD25+FOXP3+ or CD4+CD25hi+CD39+ cells.
- Naïve/Memory T lymphocytes CD4+ and CD8+ (defined as CD45RA/CD45RO)
- myeloid-derived suppressor cells, defined as cells expressing Lin-neg (CD3, CD14, CD15, CD19, CD56) /HLA-DR-/CD33+/CD11b+ in either a “lymphocyte” (small FSCxSSC) gate, or in a “monocyte” (larger FSCxSSC) gate, and as HLA-DR+/lo CD14+ cells in a large gate.
- Plasmacytoid Dendritic Cells (CD303+CD123+)
- NK cells dim (CD3-CD16+CD56+) and bright (CD3-CD16-CD56++);
- NKT cells (CD3+CD56+);
- Myeloid Dendritic cells (CD1c+ and CD141+);
- Monocytes subsets (classical CD14+CD16-, intermediate CD14+CD16+, non classical CD14+/-CD16+);
- B lymphocytes (CD19)
- Analysis of plasma cytokines (TNFalpha, TGFbeta, IL-6, IL-10) by ELISA;
- IFN signature: real-time PCR on mRNA from peripheral blood mononuclear cells (PBMCs)

- DFS of patients according to the values of the above reported immune population at baseline, after RT and according to the changes before/after RT

- Changes in immune population cell at the two time points according to the following variables:

- Site of irradiation (involving or not nodal basins, head and neck vs non-head and neck area and lymphnodes levels involved in CTV-HR vs CTV-LR)
- Volume of irradiation (expressed as cc) for primary site and nodal basin (volume received by lymphnodes classified as CTV-HR vs CTV-LR)
- Dose of irradiation (total dose received in Gy) for primary site (depending on the margin status) and nodal basin (dose received by lymphnodes classified as CTV-HR vs CTV-LR)

- Changes in immune population cells in the immunosuppressed patient subgroup in comparison with non-immunosuppressed patients

- Changes in immune population cells according to RT related toxicities as mucositis and radiodermatitis

- 2-year OS

3. SUBJECTS TO BE RECRUITED

3.1. Inclusion criteria

1. Age \geq 18 years.
2. Signed written informed consent.
3. Histologically confirmed diagnosis of cSCC
4. cSCC categorized as high risk according to ASTRO Guidelines:
 - close or positive margins that cannot be corrected with further surgery (secondary to morbidity or adverse cosmetic outcome)
 - gross perineural spread, as identified by radiological or pathological assessment
 - disease recurrence after a prior margin-negative resection
 - pathological stage T3 and T4
 - desmoplastic or infiltrative tumors in the setting of chronic immunosuppression
 - at pathological exam, cSCC involving regional lymphnodes, with the exception of a single, small (<3 cm) cervical lymph node harboring carcinoma, without extracapsular extension.
5. cSCC addressed to adjuvant radiotherapy as per clinical practice (a complete post-operative treatment should be administered with 50-54 or 60-66 Gy depending on the margin status)
6. Eastern Cooperative Oncology Group (ECOG) Performance status of 0-2.

3.2. Exclusion criteria

1. cSCC not eligible for surgery
2. cSCC not eligible for adjuvant radiotherapy for any condition depending on disease characteristics or patient characteristics, co-morbidities or refusal
3. Any concurrent investigational product, biologic, or hormonal therapy for cancer treatment
4. Concurrent treatment with chemotherapy for the purpose of cSCC cure
5. History or current evidence of any condition that, in the opinion of the treating investigator, might interfere with the subject's participation for the full duration of the trial.
6. Any major surgery, different from that planned for the protocol, in the 15 days before the protocol starting
7. Any radiotherapy treatment in the 28 days before the protocol starting
8. Pregnant or breastfeeding.

NB: patients with chronic hematological malignancies with or without ongoing treatment or patients with autoimmune diseases will be eligible for the study. They will be analyzed both in the whole series of patients and as a separate subgroup.

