1.3. IMMUNE SYSTEM IN cSCC AND IMMUNO-MODULATING EFFECTS OF RADIOTHERAPY

[figure not shown]
cSCC is a neoplasm strictly related to immunosuppression: in this context, cSCC could be multiple, recurrent and more aggressive. This statement highlights the importance to study the relationship between this tumor and circulating immune-cell and tumor microenvironment (TME). The immune mechanisms involved in tumors development are complex and related to the interplay of immunosurveillance/immunoediting and the TME that is characterized by dynamic intercellular communications via networks of chemokines, cytokines, growth factors and inflammatory remodeling enzymes. A lot of immune-circulating cells are involved in tumor growth control and in cSCC development, as neutrophil, T lymphocytes (CD8 and CD4, natural killer cells), B lymphocytes, dendritic cells, myeloid-derived suppressor cells, chemokines and cytokines (IL-6, IL-10, IL-2, IFN- γ , TGF- β) (10). This equilibrium between TME and circulating immune cells plays an important role

in patient's outcome. Moreover, oncologic treatments as chemotherapy and radiotherapy modifies and influences patient's immune system. In particular, several retrospective studies demonstrated the alterations induced by radiotherapy in different cancer subtypes and their effects on outcome. In patients affected from pancreatic, head and neck, non-small cell lung cancer and cervical cancer, radiation or chemoradiation treatments induced lymphopenia (defined as lymphocytes < 500) and the occurrence of elevated neutrophil- to- lymphocytes ratio in many patients who were characterized from worse prognosis in terms of reduced progression or disease-free survival and overall survival. Furthermore, worse outcomes were related to dose, volume and site of irradiation. For non-small cell lung cancer a connection between radiation-induced lymphopenia and Gal-1 secretion was found. Even if there are not in literature studies evaluating the relation between lymphopenia and cSCC, we can hypothesises that the same scenario could interest patients affected from neoplasm as cSCC that is also particularly dependent from patient's immune system. (11-12).

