The relation between immune system and neoplasm has become an important field of research with immunotherapy development in these last few years. Radiotherapy causes modifications on circulating immune cells and TME. In fact, irradiation provokes endothelial cells damages and inflammation causing inhibition of CD8+ T lymphocytes infiltration into tumors and immunosuppressive pathways activation. This immunosuppressive effect is represented by accumulation of radioresistant suppressor cells as macrophages, myeloid-derived suppressors cells, and regulatory T cells. But, on the other hand, irradiation can also activate the immune response through release and presentation of antigens, priming and activation of T lymphocytes, recruitment and accumulation of T cells in the tumor, enhancing inflammation and increasing IFN- γ expression (13-14). So, radiotherapy effect on immune system and TME is very complex and two-fold.

We lack studies evaluating the interplay between immune system and cSCC before and after radiation treatment, investigating the effect on TME. The aim of this study is to evaluate the effect of radiotherapy-induced lymphopenia in cSCC on outcomes and radiotherapy modifications in terms of changes in the profile of circulating immune cells.

Fig. 1 The two-fold effect of radiotherapy on cancer cells and TME

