2. STUDY OBJECTIVES AND OUTCOMES

2.1.1. Primary objective

The primary endpoint is to evaluate the impact of diminished ALC (Absolute Lymphocyte Counts) after RT on patient's outcome.

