2.1.2. Primary outcome

Primary outcome consists of disease-free survival (DFS) of patients with ALC < 500 cells/mL after radiotherapy treatment.

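### The primary DFS comparison groups patients only by ALC below 500 after RT, so lymphopenia already present at day -1 from blood cancer or immunosuppression is not separated from RT-induced lymphopenia

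*Combined protocol and SAP*

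**What the plan says.** **Eligibility.** The note closing section 3.2 admits "patients with chronic hematological malignancies with or without ongoing treatment", and also patients with autoimmune disease. Section 5.3 exempts treatment of chronic blood cancer from its ban on other anti-cancer therapy, and 5.2 permits other drugs. One high-risk criterion in 3.1 is "desmoplastic or infiltrative tumors in the setting of chronic immunosuppression".

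**Question and grouping.** Section 1.3 sets out to "evaluate the effect of radiotherapy-induced lymphopenia in cSCC on outcomes", and 2.1.1 to "evaluate the impact of diminished ALC (Absolute Lymphocyte Counts) after RT". Section 2.1.2 reads "Primary outcome consists of disease-free survival (DFS) of patients with ALC" below 500 after radiotherapy. Section 10.1 uses the same cut for Group0 (17 patients) and Group1 (25). Section 4.1 schedules two samples, day -1 and day 28 (±3) after RT, and ALC is measured on both.

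**Safeguards.** On the patients named in the 3.2 note: "They will be analyzed both in the whole series of patients and as a separate subgroup". Section 2.2.2 adds, as a secondary outcome, DFS "according to the values of the above reported immune population at baseline, after RT and according to the changes before/after RT". Section 10.2 plans a Cox regression, univariable then multivariable, and says in general terms that models adjust for clinical confounders.

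**The concern.** A patient below 500 at day -1 because of leukaemia, lymphoma or an immunosuppressant, and still below 500 at day +28, enters Group0 exactly as does one whose count fell during RT. The primary hazard ratio then mixes the two sources of lymphopenia.

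Section 1.3 says of immunosuppression that "in this context, cSCC could be multiple, recurrent and more aggressive". The same condition could therefore lower ALC and worsen DFS, and so imitate an effect of RT-induced lymphopenia. Equally, patients whose low count has nothing to do with RT and who do comparatively well would dilute a true effect. Either way, neither a positive nor a null primary result could be attributed to RT with confidence.

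**Working it through.** **1. Does any safeguard reach the primary comparison?**

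- Separate subgroup (3.2): this looks at the affected patients by themselves. The check needed is the reverse, namely whether the ALC effect persists without them. The immunosuppressed subgroup in 2.2.1 concerns immune-cell changes, not DFS.
- DFS by baseline and by change (2.2.2): separate secondary analyses, which do not adjust the primary comparison.
- Multivariable Cox (10.2): no covariate is named, and clinical variables need not include a laboratory baseline. Section 10 does not mention the day -1 sample; the T0 it defines for the secondary endpoints is 28 days after RT.

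**2. The plan's own figure.** Inputs from 10.1: HR 0.3, 5% error (taken as two-sided), 80% power, 17 and 25 patients.

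Events = (1.96 + 0.84)² / [(17×25/42²) × (ln 0.3)²] = 7.85 / (0.241 × 1.450) = 22.5, so 23. The stated 23 events reproduce.

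**3. Illustrative effect on power.** Exponential survival, Group0 median 18 months, HR 0.3, log-rank test, simulated. With 24 months of follow-up per patient (4.3), expected events are 17×0.603 + 25×0.242 = 16.3. Assumption: k = 2, 4 or 6 of the 17 Group0 patients are low because of disease or drug.

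| Hazard of the k patients, relative to Group1 | Power, 24 months (none affected: 69%) | Power, 24-48 months (none affected: 80%) |
|---|---|---|
| 1 times | 59 / 48 / 37% | 69 / 57 / 44% |
| 2 times | 65 / 60 / 54% | 75 / 70 / 64% |
| 3 times | 68 / 67 / 66% | 79 / 78 / 77% |

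**4. Illustrative false-positive rate.** Assume ALC has no effect, a common monthly hazard of 0.02048 (which gives 16.3 events among 42 at 24 months), and affected patients at 2 to 3 times that hazard. The nominal 5% becomes 4-5% if they are split equally between ALC groups, about 6-6.5% if split 3:1 or 4:2, and 5.5-15% if all are in Group0, the worst case.

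**5. Price of adjusting for day -1 ALC.** With correlation r between day -1 ALC and the ALC group (assumed), the standard error grows by 1/√(1−r²), and power = Φ(√[D × 0.241 × (1−r²)] × 1.204 − 1.96), where D is events and 1.204 = −ln 0.3.

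| r | SE factor | Power, D = 16.3 | Power, D = 23 |
|---|---|---|---|
| 0 | 1.00 | 66% | 81% |
| 0.3 | 1.05 | 62% | 77% |
| 0.5 | 1.15 | 54% | 69% |
| 0.7 | 1.40 | 40% | 53% |

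**6. Price of the exclusion analysis.** Patients with blood cancer or on lymphocyte-lowering treatment may be in either ALC group. If k leave each group, 24-month power is about 65/61/55%. Against leaving them in (step 3), that gains 6/13/18 points at 1 times Group1's hazard, is about level at 2 times, and loses 3/6/11 points at 3 times. The reason for this analysis is attribution, not power.

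**The case against.** The strongest reply is that the question is prognostic. Section 4.1 words the aim as outcome by post-radiation lymphocyte count, and 2.1.2 is compatible with that; on this reading, grouping by the day +28 count whatever its cause is intended. This stands in part. A reader might infer that the primary result cannot answer the protocol's aim. The documents do not support that much, because they word the aim in two ways. The point holds for the RT-induced wording of 1.3 and 2.1.1.

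Second, inclusion is deliberate and partly handled, and exclusion 3 in 3.2 (concurrent biologic therapy for cancer) may remove some treated patients, although it sits uneasily with the note. This limits the number affected but does not reach the primary model.

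Third, the figures rest on an assumed k; six patients would be 35% of Group0. The largest power losses require affected patients to share Group1's good prognosis, which fits poorly with section 1.3. The largest false-positive rate requires all of them to be in Group0. Both objections stand.

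Fourth, a reader might infer that drug exposure between the two samples goes unrecorded. The schedule has no medication row, but medical history is taken at screening, section 6 collects other treatments, 8.4 requires source records, and the eCRF is not among the documents. What is shown is missing detail, not missing data.

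**Conclusion.** The point holds in limited form. The primary grouping counts pre-existing lymphopenia as lymphopenia after RT, in a population where the plan expressly allows a non-RT cause, and no stated analysis separates the two in the primary comparison. That is more than an unnamed covariate, because day -1 ALC is what distinguishes a diminished count from one that was low already.

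Neither the size nor the direction of bias can be fixed: the documents give no expected number of such patients and no baseline ALC distribution. Under the assumptions shown, the effect ranges from negligible (1-3 points of 24-month power at 3 times Group1's hazard; false-positive rate 4-6.5% unless all are in Group0) to serious (power 37%, or a false-positive rate of 15%, at the extremes). The documents do not support a claim that the result is biased in a particular direction, or that these patients should be ineligible. The change should be made before DFS data are examined; it is no reason to hold the study.

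**What to change.** In 10.2:

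1. Report the planned univariable DFS result by ALC group.
2. Beside it, name day -1 ALC as the first covariate in the multivariable primary DFS Cox model, with at most one further covariate, since only about 16-23 events are expected.
3. Pre-specify a DFS sensitivity analysis that excludes patients with haematological malignancy or on lymphocyte-lowering treatment from both ALC groups.

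This takes a few sentences and needs no extra visit, sample or patient, because day -1 ALC is already measured. The cost is the precision shown in steps 5 and 6, which is why the univariable result stays alongside. Adjustment for day -1 ALC cannot account for a drug started between the samples.

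Optional clarifications: record haematological and immunosuppressive drugs with start and stop dates at day -1 and day +28 (one schedule row and its eCRF page, if not already there), which would also identify patients for item 3; and cross-refer exclusion 3 to the note in 3.2.

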4. STUDY DESIGN

4.1. Overview

The patients enrolled in the study are affected form cSCC classified at high risk and addressed to surgery and subsequent adjuvant RT according to clinical practice. The aim of the study is to evaluate patients' outcome according to the post-radiation lymphocytes count and to the changes induced in the immune cell population by a loco-regional treatment as radiotherapy.

The way to objectivate these results is to collect some blood samples and analyze them.

The study comprises blood samples collection performed at two time points:

- at baseline (day -1) before adjuvant RT;
- at day 28 (+/- 3) after RT completion.

At any timepoints blood samples will be analyzed for immune cell population detailed in 2.1.2 and 2.2.2 paragraphs.

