4.3 Duration of study

The duration of the treatment is limited by the completion of adjuvant radiotherapy.

This study will take 24 months to conclude the enrollment of 42 patients.

Follow up of the patients will be carried out according to clinical practice, with periodic visits and

instrumental assessments. Patients' follow-up will continue for 24 months after the end of radiation and patients still alive will be considered as censored.

Therefore, the whole duration of the study (enrollment + follow up) will be 48 months.

First results will be evaluated in an interim-analysis (primary and secondary objectives of before-after RT change in immune populations) at 24 months.

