10.1 Sample size calculations

To test the Hazard Ratio between Group0 (patients with ALC less than 500 cells/mL) and Group1 (patients with ALC greater than 500 cells/mL) of 0.3 with type I error rate of 5% and power of 80%, we need a minimum of 23 total events which in our hypothesis of median survival time in Group 0 equal to 18 months, 5% censoring rate and whole duration of the study of 4 years correspond to 42 patients, 17 in the Group0 and 25 in the Group1..

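### The ALC group is known only from the day-28 sample after RT, but the plan gives no DFS origin or events and no landmark for the Cox comparison

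*Combined protocol and SAP*

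**What the plan says.** Section 2.1.2 sets the endpoint: "Primary outcome consists of disease-free survival (DFS) of patients with ALC < 500 cells/mL after radiotherapy treatment". Section 4.1 allows two blood draws, one the day before RT and one "at day 28 (+/- 3) after RT completion". Sections 2.2.2, 6 and 11 repeat this timing. Section 10 takes its expected 40% share of low-ALC patients at one month after RT, which matches the second draw. A patient's group is therefore unknown until about four weeks after RT.

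No section says when the DFS clock starts or which events count. Section 10.2 names a Cox model, univariable and then multivariable, for DFS and OS. It mentions no landmark, delayed entry or time-dependent ALC term, and does not say what happens to a patient who relapses, dies or misses the draw before day 28. Its T0 at 28 days after RT belongs to the mixed models for the secondary endpoints, not to DFS.

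The one place that counts follow-up time is Section 4.3: "follow-up will continue for 24 months after the end of radiation". Section 4.2 puts the first scheduled imaging at 3 months after RT, with clinical examinations every 3 months in the first year.

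**The concern.** The exposure is measured after the point from which follow-up is counted, so the analyst must decide what to do with failures in between. The plan leaves that decision open until the data are in hand. Each of the two obvious choices has its own fault.

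- **Keep early relapses that were still sampled.** Their group rests on a count drawn after the event. Section 1.3 says that chemotherapy and radiotherapy alter the immune system, and Section 11 anticipates further treatment at progression. An early relapse, or its treatment, could therefore lower the count that defines the group. This favours the study hypothesis.
- **Keep only patients who were relapse-free at the sample, but leave the clock at the earlier origin.** Both groups then carry a stretch in which nobody could fail. Their DFS curves are too high, and Section 2.1.2 words the primary outcome as the DFS of the low-ALC group.

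The design needs only 23 events, so a few patients handled one way or the other can matter.

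**Working it through.** **Inputs.** From Section 10.1: hazard ratio 0.3 (Group 1, ALC above 500, against Group 0, ALC below 500), type I error 5% (two-sided assumed), power 80%, and "median survival time in Group 0 equal to 18 months, 5% censoring rate and whole duration of the study of 4 years". The 5% censoring is read as 0.05 per year. Constant hazards are assumed.

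**The plan's own figures.**
- Events (Schoenfeld): (1.960 + 0.842)² / [(17/42)(25/42)(ln 0.3)²] = 7.849 / (0.2409 × 1.4496) = 22.5, rounded up to 23. This agrees with "we need a minimum of 23 total events".
- Yearly hazards: λ0 = ln 2/1.5 = 0.462 and λ1 = 0.3 × 0.462 = 0.139.
- Probability of an observed event by T = 4 years, with c = 0.05: P = λ/(λ+c) × [1 − exp(−(λ+c)T)], giving P0 = 0.786 and P1 = 0.389.
- Weighted mean: (17 × 0.786 + 25 × 0.389)/42 = 0.550. N = 23/0.550 = 41.8, rounded up to 42, as in "42 patients, 17 in the Group0 and 25 in the Group1". Expected events in 42 patients are 23.1, which gives 81.1% power.

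**Events before the sample, from end of RT.** 28 days is 0.92 months.
- Group 0: 17 × [1 − 2^(−0.92/18)] = 17 × 0.0348 = 0.59.
- Group 1: 25 × [1 − 2^(−0.3×0.92/18)] = 25 × 0.0106 = 0.26.
- Total about 0.9 of 42 (0.8 to 0.9 over days 25 to 31). The chance of at least one is 1 − exp(−0.85) = 57%.

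**DFS level if early failures are dropped and the clock is not reset.** With g months from origin to sample, the 24-month figure becomes exp(−λ(24−g)) instead of exp(−24λ), with λ = ln 2/18 per month in Group 0 and 0.3 times that in Group 1.

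| g (months) | Group 0, true 39.7% | Group 1, true 75.8% | Events before sample |
|---|---|---|---|
| 0.92 (end of RT) | 41.1% (+1.4) | 76.6% (+0.8) | 0.9 |
| 2.2 (assumed) | 43.2% (+3.5) | 77.7% (+2.0) | 2.0 |
| 4.5 (assumed) | 47.2% (+7.5) | 79.8% (+4.0) | 4.0 |

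**Effect on the hazard ratio** (Cox simulation, 4,000 runs per scenario, 2-year and 4-year horizons).
- Early failures dropped, clock not reset: the hazard ratio stays at about 0.30 and type I error at 4 to 5%, matching the landmark analysis within simulation error. The guarantee time is the same in both groups.
- Early relapses kept, in a worst case where each one with ALC above 500 is counted as below 500: with no true effect, type I error is about 6% from end of RT (hazard ratio 0.87 to 0.91). It is 12 to 13% from RT start (0.72 to 0.78) and 18 to 22% from surgery (0.61 to 0.69).

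**Events and power after a landmark** (42 patients, 4-year horizon).

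| DFS would otherwise start at | Days to sample | Events lost | Events left | Power |
|---|---|---|---|---|
| End of RT | 28 | 0.85 | 22.2 | 79.4% |
| RT start (6 weeks of RT assumed) | 70 | 2.1 | 21.0 | 76.8% |
| Surgery (6 to 8 weeks before RT assumed) | 112 to 129 | 3.3 to 3.7 | 19.8 to 19.4 | 74.0 to 72.9% |

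**The case against.** The strongest reply concerns size. Section 4.3 counts follow-up from the end of radiation, and from there the gap is four weeks, with under one expected event. Few relapses would even be dated that early, because the first scheduled imaging and the 3-monthly examinations come later. A patient who dies before day 28 without a sample cannot be grouped at all. All of this stands, and it makes 0.9 events more likely too high than too low.

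A reader might infer that 24-month DFS will be overstated by 3.5 to 7.5 points and that 2 to 4 patients will be affected. The documents do not support this as an expectation. It needs a clock starting at RT start or surgery, which no section states, and intervals that are partly assumed. A recurrence between surgery and RT might also make adjuvant RT inapplicable under Section 3, so such patients might never be among the 42.

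A reader might also infer that guarantee time biases the hazard ratio. It does not, because both groups share it. Only the reverse-exposure route can bias the ratio, and the 12 to 22% error rates need both an earlier origin and a worst-case misclassification that nothing in the documents supports. Nor do the two harms add up, since one arises when early failures are dropped and the other when they are kept.

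Finally, 24-month DFS is not a specified estimand; only OS has a 2-year definition. It serves here to show the size of the distortion. What remains is that the origin, the events and the handling of early failures are undefined for the primary comparison.

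**Conclusion.** The concern holds as a gap in the analysis plan, with a small effect on the one anchor that the documents give. From end of RT, about 0.9 of 42 patients would have an event before the sample. Without a clock reset, 24-month DFS would read about 1.4 points too high in Group 0 and 0.8 in Group 1. From RT start or surgery, the figures would be about 2 to 4 patients and 3.5 to 7.5 points in Group 0. These are scenarios, not expectations.

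The figures rest on constant hazards, the plan's 18-month median and hazard ratio of 0.3, and assumed intervals for the earlier origins. The power figures also rest on the plan's 4-year horizon and censoring read as 5% per year. If each patient is instead followed for the 24 months in Section 4.3, the same model gives 15.6 events and 65% power before any landmark, and 14.8 events and 62% after one from end of RT. That shortfall is a separate matter.

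The change should be made because it is standard, costs little, and settles before the data are seen a choice that could otherwise be made afterwards.

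**What to change.** In Section 10.2:

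1. State which events count for DFS.
2. Make the ALC-group comparisons of DFS and OS landmark analyses. Time zero is the actual date of the day-28 sample, and the population is patients who are sampled, alive and recurrence-free at that date.
3. Report the number of patients excluded before the landmark and the reason for each. The Section 11 schedule lists no disease-status entry at day +28, so the status used at the landmark should be recorded.
4. Restate expected events and power for the landmark population.

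The cost is wording, about one lost event, and power of about 79% instead of 80% if DFS would otherwise run from end of RT. With an earlier origin, power is about 73 to 77%. The result then applies to patients still recurrence-free about four weeks after RT. Keeping 23 post-landmark events on the 4-year assumptions would take about 44 patients (42 × 23/22.24 = 43.4), or 46 to 50 with an earlier origin. The loss does not justify enrolling more; restating the power is enough.
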